6.4.1 Primary Efficacy Endpoint

The primary endpoint for the Maintenance Phase is Week 62 remission among patients *with a clinical response at Week 10. Patients who are randomized into the Maintenance Phase (i.e., clinical responders at Week 10) will be evaluated.* The difference in remission rates between the etrolizumab and placebo arms will be compared using the Cochran-Mantel-Haenszel test statistic stratified by concomitant treatment with corticosteroids at baseline (yes/no), concomitant treatment with immunosuppressants after Week 10 (yes/no), and baseline disease activity (MCS ≤ 9 , MCS ≥ 10). The absolute difference in remission rates and 95% CIs for the point estimate will be provided.

6.4.2 Secondary Efficacy Endpoints

The secondary efficacy endpoints for the Maintenance Phase are as follows:

- Proportion of patients *in* clinical remission at Week 62 among patients in clinical remission at Week 10
- Proportion of patients in clinical remission at Week 62
- *Proportion of patients in remission at Week 62 among patients in remission at Week 10*
- Proportion of patients with improvement in endoscopic appearance of the mucosa at Week 62
- Proportion of patients in endoscopic remission at Week 62
- Proportion of patients in histologic remission at Week 62
- *Change from baseline in rectal bleed subscore at Week 6*
- *Change from baseline in stool frequency subscore at Week 6*
- Proportion of patients in corticosteroid-free remission at Week 62 (off corticosteroids for at least 24 weeks prior to Week 62) in patients who were receiving corticosteroids at baseline

- Proportion of patients in corticosteroid-free clinical remission at Week 62 (off corticosteroids for at least 24 weeks prior to Week 62) in patients who were receiving corticosteroids at baseline
- Change from baseline to Week 62 in UC bowel movement signs and symptoms as assessed by the UC-PRO/SS measure
- Change from baseline to Week 62 in UC abdominal symptoms as assessed by the UC-PRO/SS measure
- Change from baseline to Week 62 in health-related QOL, as assessed by the overall IBDQ score.

All the responder/remitter type secondary endpoints will be analyzed in the same fashion as the primary endpoint. The continuous secondary endpoints will be analyzed using an analysis of covariance (ANCOVA) model with Week 10 remission status, concomitant treatment with corticosteroids, concomitant treatment with immunosuppressants, baseline disease activity ($MCS \leq 9$, $MCS \geq 10$) as stratification variables, and the baseline value of the studied measure as a covariate.

6.4.3 Exploratory Efficacy Endpoints

The exploratory efficacy endpoints are as follows:

- *Proportion of patients with a clinical response at Week 62 among patients with clinical response at Week 10*
- *Proportion of patients with remission at Week 62 among patients in clinical remission at Week 10*
- Proportion of patients in corticosteroid-free clinical remission at Week 62 (off corticosteroids for at least 12 weeks prior to Week 62) in patients who are receiving corticosteroids at baseline
- *Proportion of patients with change in histologic disease activity from baseline to Week 10 and Week 62*
- *Proportion of patients with improvement in histologic and/or endoscopic disease activity*
- Proportion of patients with improvement in endoscopic appearance of the mucosa at Week 10
- Proportion of patients with endoscopic remission at Week 10
- Frequency and duration of hospitalizations from Week 10 to Week 62
- *Proportion of patients with response, remission and corticosteroid-free endpoints as determined by the mMCS*

The endpoints listed above will be analyzed *using the same statistical methods* as the primary endpoint.

- Change in health utilities, as assessed by the EQ-5D, from Week 10 to Week 62
- Change in *histologic disease activity*, from *baseline to Week 10 to Week 62*

Etrolizumab—F. Hoffmann-La Roche Ltd
112/Protocol GA29102, Version 7

These endpoints will be analyzed *using the same statistical methods* as the UC/PRO and IBDQ continuous endpoints.

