- If corticosteroids are being tapered, the dose has to be stable for at least 2 weeks immediately prior to Day 1

Such patients should continue stable doses of their background corticosteroid until Week 10, at which point a corticosteroid taper will be initiated.

Initiation of corticosteroid or an increase in corticosteroid dose above the patients' entry dose (up to a maximum of 30 mg/day prednisone [or equivalent]) will not be permitted during screening. Use of budesonide will be allowed at stable doses (≤ 9 mg) provided that the dose has been stable for ≥ 4 weeks prior to Day 1. Oral 5-ASA treatment and probiotics for the treatment of UC may be continued at a stable dose as long as the dose(s) had been stable for ≥ 4 weeks and ≥ 2 weeks, respectively, prior to Day 1. Certain concomitant treatments are prohibited (see Section 4.1.2 for list of all prohibited concomitant treatments).

A total of approximately 350 patients will be recruited (see Figure 1) from approximately 125 sites. The study will be divided into:

- Screening period of up to 35 days (for details see Section 4.5.2.1)
- Open-label etrolizumab treatment period of 10 weeks (Induction Phase)
- Double-blind treatment period of 52 weeks (Maintenance Phase)
- Safety follow-up period of 12 weeks

All patients entering the study will receive induction treatment with open-label etrolizumab (105 mg SC Q4W) for 10 weeks. Eligibility for entry into the Maintenance Phase will be determined between Weeks 10 and 12. Patients who achieved a clinical response at Week 10 (see Table 1 for definition of clinical response) will be randomized in a 1:1 ratio by Week 12 into the Maintenance Phase and will receive either etrolizumab (105 mg SC Q4W) or placebo ($n \approx 105$ for each arm). Randomization will be stratified by their remission status at Week 10, concomitant treatment with corticosteroids (including budesonide) at baseline, concomitant treatment with immunosuppressants after Week 10, and disease activity measured during screening ($MCS \leq 9/MCS \geq 10$).

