3.1.1.1 Definition of Clinical Relapse

Clinical relapse is defined as an:

- Increase in partial Mayo Clinic Score (pMCS) ≥ 3 points compared with induction timepoint (Week 10) AND absolute pMCS ≥ 5 AND endoscopic subscore ≥ 2

If a patient meets criteria for clinical relapse during the Maintenance Phase of the study, he or she may withdraw from this study and enroll in Part 1 (OLE) of Study GA28951 to receive open-label etrolizumab treatment, if eligible.

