#### **4.4.3 Exploratory Efficacy Endpoints**

Exploratory endpoints detailed in the protocol will also be analyzed. Binary endpoints will use the same statistical methods used for the primary endpoint. Continuous endpoints will use the same statistical methods used for the change from baseline key secondary endpoints.

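### Hospitalisation frequency and duration have no stated analysis that clearly fits them, and neither available route accounts for time at risk

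*Protocol*

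**What the plan says.** Protocol 6.4.3 lists "Frequency and duration of hospitalizations from Week 10 to Week 62" with eight other exploratory endpoints and closes the list with: "The endpoints listed above will be analyzed *using the same statistical methods* as the primary endpoint". Protocol 6.4.1 sets out that primary method: a CMH test on remission rates, stratified by baseline corticosteroid use, immunosuppressant use after Week 10 and disease activity, with an absolute difference and 95% CI. Each of the other eight bullets is worded as a proportion of patients. The hospitalisation bullet is not.

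Protocol 6.4 leaves further definitions of exploratory endpoints to the SAP. Study SAP 2.2 drops several protocol endpoints that have no comparator, and 2.2.1 keeps the hospitalisation endpoint without defining it. Study SAP 4.4.3 then gives two general rules: "Binary endpoints will use the same statistical methods used for the primary endpoint" and "Continuous endpoints will use the same statistical methods used for the change from baseline key secondary endpoints". It does not say which applies to hospitalisations.

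Patients can leave before Week 62. On clinical relapse (Protocol 3.1.1.1) a patient has the option that "he or she may withdraw from this study and enroll in Part 1 (OLE) of Study GA28951", and Protocol 3.1.1.2, 4.3.2.2 and 4.5.2.3.1 offer the same transfer after several kinds of permitted rescue.

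**The concern.** A CMH test on proportions needs a yes/no outcome for each patient. Number of admissions and days in hospital are not yes/no, and neither document defines a binary version such as any hospitalisation. The SAP's second route is built for scores measured at baseline and again at a visit; an event counted from Week 10 onward has neither.

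The second difficulty is exposure. Patients who transfer to the extension skip this study's safety follow-up (Protocol 4.5.2.4), and their adverse events are then reported under the other study (Protocol 5.3.1). Their observation here ends at exit. An arm that loses patients sooner has less time in which to record admissions, and a comparison that ignores this mixes the treatment's effect on hospitalisation with its effect on staying in the trial. At stake is the reading of one exploratory result, on an outcome that Protocol 1.1 counts among the goals of treatment.

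**Working it through.** The plan states no expected hospitalisation rate, exit rate or power for this endpoint, so there is no figure to reproduce.

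**Fit of method to data**

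- *CMH (Protocol 6.4.3 and 6.4.1; SAP rule for binary endpoints).* Fits only if frequency means patients with at least one hospitalisation. Does not fit days in hospital. No exposure term.
- *Change from baseline (SAP rule for continuous endpoints).* The key secondary endpoints of this type are the UC-PRO/SS domain scores, analysed by a mixed model for repeated measures with visit terms and a baseline covariate (project SAP 4.4.2.3.1). Baseline is the last assessment before the first induction dose (study SAP 2.2), so admissions after Week 10 have no baseline value. No exposure term.
- *Missing-data rules.* Non-responder imputation (Protocol 6.4) covers response and remission endpoints. Project SAP 4.8 covers scores and diary dates. Neither applies to a count or to days.
- *Person-time elsewhere.* Project SAP 4.7.1 plans adverse event and SAE rates per 100 patient-years for this study, as a safety summary.

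**Size of a possible bias (illustration; all rates below are assumptions)**

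Follow-up is taken as 1 year (52 weeks). A fraction *f* of each arm leaves early, uniformly over the year and independently of hospitalisation risk. Admissions are Poisson with rate λ per patient-year, the same in both arms.

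Mean follow-up: T = (1 − f) × 1 + f × 0.5. With equal λ, the unadjusted etrolizumab/placebo count ratio is T_etro / T_pbo.

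| Exit, placebo / etrolizumab | T_pbo | T_etro | Count ratio |
|---|---|---|---|
| 0% / 0% | 1.00 | 1.00 | 1.00 |
| 30% / 30% | 0.85 | 0.85 | 1.00 |
| 40% / 20% | 0.80 | 0.90 | 0.90/0.80 = 1.125 |
| 50% / 30% | 0.75 | 0.85 | 0.85/0.75 = 1.133 |
| 60% / 30% | 0.70 | 0.85 | 0.85/0.70 = 1.214 |

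Dividing by person-time returns 1.00 in every row.

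Proportion with any hospitalisation, the scale on which CMH would work:

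P = (1 − f)(1 − e^(−λ)) + f[1 − (1 − e^(−λ))/λ]

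- Smallest difference among the three unequal-exit pairs, λ = 0.05 with 40%/20%: 3.91% placebo, 4.39% etrolizumab, +0.48 points.
- Largest, λ = 0.20 with 60%/30%: 12.87% placebo, 15.50% etrolizumab, +2.63 points.

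With a true benefit, say λ = 0.12 on etrolizumab and 0.20 on placebo (rate ratio 0.60) and exits of 50%/25%: unadjusted ratio = (0.12 × 0.875)/(0.20 × 0.75) = 0.105/0.150 = 0.70. The person-time ratio stays at 0.60.

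A simulation of 20,000 trials with 105 per arm, no true effect and 50%/25% exits gave count ratios of 1.171 (λ = 0.10) and 1.167 (λ = 0.20), and person-time ratios of 1.003 and 1.001. An unstratified two-sided 5% test on any hospitalisation rejected in 6.4% and 7.2% of trials, against 5.4% with no exits at λ = 0.10.

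**The case against.** The strongest reply is that the SAP governs the detail and does not repeat the protocol's assignment. A reader might infer that both documents prescribe CMH for hospitalisations. They do not: only the protocol does, and the SAP leaves the endpoint unclassified. That turns a wrong rule into a gap in the SAP but does not close it, because neither SAP route suits duration.

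Second, frequency need not mean a count. Protocol 6.5.1 uses the word for serious infections and injection-site reactions alongside incidence summaries. Read as patients with any hospitalisation, CMH would fit that half of the endpoint. This stands; duration and time at risk remain unaddressed.

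Third, a reader might conclude that the planned analysis is biased. The documents do not support that. Bias needs exit to differ by arm, no exit rates are given, relapsing patients have the option rather than the duty to leave, and study SAP 4.4 says patients on permitted rescue will be asked to continue. Nor does any single pair of follow-up times settle the size: mean follow-up of 0.65 against 0.80 years would give 0.65/0.80 = 0.81, but those inputs are no better founded than others, and raw counts are not the scale on which CMH works.

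Fourth, the SAE rates per 100 patient-years give a partial person-time view, since most admissions for an adverse event are SAEs (Protocol 5.3.5.10 lists exceptions). True, but that is not an analysis of this endpoint.

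Finally, an offset assumes that leaving is unrelated to hospitalisation risk, whereas exit here can follow relapse. Person-time rates may therefore keep some bias. This limits what the remedy can achieve.

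**Conclusion.** The concern holds in a limited form. The protocol's stated rule does not fit duration and fits frequency only on one reading; the SAP does not resolve this; and neither route accounts for time at risk. That part rests on the text alone.

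The bias is conditional. If placebo patients leave sooner, unadjusted comparisons lean against etrolizumab. Under assumed exits of 40-60% on placebo and 20-30% on etrolizumab with no true effect, the count ratio is about 1.13 to 1.21, and the difference in any hospitalisation is about 0.5 to 2.6 points at assumed rates of 0.05 to 0.20 per patient-year. With equal exits there is none. The calculation also assumes uniform exit unrelated to hospitalisation risk.

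Severity is low: the endpoint is exploratory, outside multiplicity control, and has no bearing on the sample size or the primary conclusion.

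**What to change.** In the SAP:

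- Define the endpoint as number of admissions and total days in hospital. State whether all-cause or UC-related, and which admissions count, since Protocol 5.3.5.10 excludes some from adverse event reporting.
- Analyse the number of hospitalisations by a negative binomial or Poisson model with log time at risk (Week 10 to Week 62 or exit) as offset and the three stratification factors as covariates, collapsed if sparse.
- Report hospital days per patient-year by arm. A rank test on unadjusted days should not be used, because it ignores exposure.
- Reconcile Protocol 6.4.3 with study SAP 4.4.3 so that one rule applies.
- Note that exit driven by relapse may leave residual bias even after adjustment.

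The cost is a short SAP paragraph and a little more analysis work. No new data are needed: Protocol 5.3.5.10 already has duration of hospitalisation recorded on the eCRF. The main downside is that the model may be unstable if events are few.

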6.5 SAFETY ANALYSES

The safety analyses will include all patients who received at least one dose of study drug in the Induction Phase. Separate summaries of adverse events will be provided for the open-label Induction Phase and the Maintenance Phase.

Safety will be assessed through descriptive summaries of adverse events, laboratory test results (serum chemistry, hematology including complete blood count with differential and platelet counts, and urinalysis), and the incidence of antibodies to etrolizumab.

Additional details will be provided in the SAP.

6.5.1 Adverse Events

Verbatim descriptions of treatment-emergent adverse events will be coded and their incidence will be summarized by treatment arm, as appropriate. A treatment-emergent adverse event is defined as any new adverse event reported or any worsening of an existing condition on or after the first dose of study drug. In addition, separate summaries will be generated for serious adverse events, deaths, and adverse events leading to discontinuation of study drug. Adverse events will be summarized by mapped term, appropriate thesaurus level, and toxicity grade.

Analyses will be performed for:

- Systemic hypersensitivity events
 - Specific analyses will be performed for anaphylactic reactions using the anaphylactic reaction Sampson's criteria (see [Appendix 8](#)).
- Serious infections
 - The frequency of serious infections, in particular GI infections, will be summarized for each treatment arm.
- Opportunistic infections
 - The occurrence of opportunistic infections will be summarized for each treatment arm.
- Malignancies
 - Events that occur in the Neoplasms, Benign, Malignant, and Unspecified (Including Cysts and Polyps) System Organ Class will also be summarized for each treatment arm.
- Injection-site reactions
 - The frequency of injection-site reactions will be summarized for each treatment arm.

6.5.2 Laboratory Tests

Descriptive summaries of laboratory values at baseline and throughout the study will be tabulated by treatment arm. For selected parameters, changes from baseline and the proportion of patients experiencing clinically significant changes relative to baseline will be summarized by treatment arm.

The number and percentage of patients with serum antibodies to etrolizumab at baseline and during the study will be tabulated by treatment arm.

6.6 PHARMACOKINETIC, PHARMACODYNAMIC, AND BIOMARKER ANALYSES

For PK assessment, group average serum etrolizumab concentration versus time data will be tabulated and plotted. The serum pharmacokinetics of etrolizumab will be summarized with a mean serum concentration at steady state (trough) and at the primary endpoint time (Week 62). Estimates for these parameters will be tabulated and summarized (mean, SD, coefficient of variation, median, minimum, and maximum).

Additional PK analyses may be conducted as appropriate.

PD and biomarkers analyses will include examination of changes over time in exploratory biomarkers after treatment. Results will be summarized descriptively.

7. DATA COLLECTION AND MANAGEMENT

7.1 DATA QUALITY ASSURANCE

Sponsor, contract research organization (CRO), and Data Management vendor will be responsible for the data management of this study, including quality checking of the data. Sites will be responsible for data entry into an eCRF via the EDC system. In the event of discrepant data, data queries will be issued to the sites and resolved by the sites via the EDC system. The Sponsor will produce an EDC Study Specification document that describes the quality checking to be performed on the data. In addition, eCRF Help Text will be provided to the sites through the EDC system. eCRFs and correction documentation will be maintained in the EDC system's audit trail.

Central laboratory data will be transferred directly to the Sponsor with use of the Sponsor's standard procedures to handle and process the electronic transfer of these data.

7.2 ELECTRONIC CASE REPORT FORMS

eCRFs are to be completed using a Sponsor-designated EDC system. Sites will receive training and have access to Help Text in the Medidata RAVE for appropriate eCRF completion. eCRFs will be submitted electronically to the Sponsor and should be handled in accordance with instructions from the Sponsor.

All eCRFs should be completed by designated, trained site staff. eCRFs should be reviewed and electronically signed and dated by the investigator or a designee.

At the end of the study, the investigator will receive patient data for his or her site in a readable format on a compact disc that must be kept with the study records. Acknowledgement of receipt of the compact disc is required.

7.3 ELECTRONIC PATIENT-REPORTED OUTCOME DATA

Patient-reported data will be collected electronically through use of electronic devices provided by an ePRO vendor. The electronic device (e-diary) is designed for entry of data in a way that is attributable, secure, and accurate, in compliance with FDA regulations for electronic records (21 Code of Federal Regulations, Part 11). The data will be transmitted to a centralized database at the ePRO vendor. The data from the ePRO devices are available for view access only via secure access to a Web portal provided by the ePRO vendor. Only identified and trained users may view the data, and their actions become part of the audit trail. The Sponsor will have view access only. Regular data transfers will occur from the centralized database at the vendor to the database at the Sponsor.

Once the study is complete, the ePRO data, audit trail, and trial and system documentation will be archived. The Sponsor will receive all data entered by patient on the e-diary and all the study documentation.

Details regarding patient-reported data and the electronic device are available in the Study Reference Manual. System backups for data stored by the Sponsor and records retention for the study data will be consistent with the Sponsor's standard procedures.

7.4 SOURCE DATA DOCUMENTATION

Study monitors will perform ongoing source data verification to confirm that critical protocol data (i.e., source data) entered into the eCRFs by authorized site personnel are accurate, complete, and verifiable from source documents.

Source documents (paper or electronic) are those in which patient data are recorded and documented for the first time. They include, but are not limited to, hospital records, clinical and office charts, laboratory notes, memoranda, PRO questionnaires, evaluation checklists, pharmacy dispensing records, recorded data from automated instruments, copies of transcriptions that are certified after verification as being accurate and complete, microfiche, photographic negatives, microfilm or magnetic media, X-rays, MRIs, ECGs, patient files, and records kept at pharmacies, laboratories, and medico-technical departments involved in a clinical trial.

Before study initiation, the types of source documents that are to be generated will be clearly defined in the Trial Monitoring Plan. This includes any protocol data to be

entered directly into the eCRFs (i.e., no prior written or electronic record of the data) and considered source data.

Source documents that are required to verify the validity and completeness of data entered into the eCRFs must not be obliterated or destroyed and must be retained per the policy for retention of records described in Section 7.6.

To facilitate source data verification, the investigators and institutions must provide the Sponsor direct access to applicable source documents and reports for trial-related monitoring, Sponsor audits, and IRB/EC review. The investigational site must also allow inspection by applicable health authorities.

7.5 USE OF COMPUTERIZED SYSTEMS

When clinical observations are entered directly into an investigational site's computerized medical record system (i.e., in lieu of original hardcopy records), the electronic record can serve as the source document if the system has been validated in accordance with health authority requirements pertaining to computerized systems used in clinical research. An acceptable computerized data collection system allows preservation of the original entry of data. If original data are modified, the system should maintain a viewable audit trail that shows the original data as well as the reason for the change, name of the person making the change, and date of the change.

